2.1. OBJECTIVES

2.1.1. PRIMARY OBJECTIVE:

• To estimate the overall, age and gender specific prevalence of HPV in the oropharynx in patients undergoing tonsillectomy for non-malignant conditions

2.1.2. SECONDARY OBJECTIVES:

- To compare the HPV oropharynx prevalence between different sites—in order to identify the different reservoirs of HPV infection
- To describe the distribution of HPV seropositivity in the study population by age and gender
- To describe HPV-type distribution overall by age, gender, and sampling site
- To describe distribution by age and gender of patients who are both HPV PCR positive and anti-HPV L1 sero-positive – predicting persistent HPV infection
- To provide preliminary estimates of the clearance and persistence of HPV infection and antibodies in the oropharynx, as detected in follow-up oral fluid, finger tips/nail brushings and urine samples
- To assess the presence of anti-L1 HPV antibodies in saliva as a marker of vaccination or previous infection in the oral cavity
- To assess the presence of HPV in the urine
- To assess the presence of HPV in finger tips/nail brushings
- To provide preliminary evaluation of the performance of potential non-invasive tests for the detection of HPV infection in the mouth against HPV detection rates in tonsillectomy and oropharyngeal scrapes
- To identify the change in overall prevalence and distribution of HPV in tonsils over time, and to describe preliminary data on age and gender specific changes over time
- To provide preliminary data on the potential effect of HPV vaccination in the prevention of oral infection

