7. STUDY PROCEDURES AND SAMPLE COLLECTION

All samples should be collected in accordance to the study procedure manual developed by GSK with details of sample collection kits, volume of samples to be collected and storage temperature requirements.

For a patient to be eligible for inclusion in the data analysis, the following samples are a minimum requirement:

- Oral samples
- Blood
- Oropharyngeal brushings
- Tonsils

 After written consent is obtained, the patients (above 16 years old only) will complete a short study questionnaire including age, gender, history of tobacco/alcohol use, sexual history including age of start of sexual intercourse, lifetime numbers of sexual partners, engagement in oral sex and lifetime number of oral sex partners etc.

- 2. An HPV vaccination history will also be taken. Consent/assent will also be taken from the patient, parent(s) or their guardian(s), if applicable, to obtain the patient's HPV vaccination status from vaccine and medical health records from their GP and/or other relevant health and educational authorities. The data requested will include confirmation of HPV vaccination status, including dates, number of doses and the type of vaccine given.
- 3. Oral fluid samples will be collected for HPV PCR and HPV antibody tests, using an oral rinse and an exudate collection device respectively.
- 4. A 20 30 ml urine sample will be collected for HPV PCR test.
- 5. Blood serum will be taken for HPV and biomarker serology tests. This can be taken after the patient has been anaesthetised if necessary. 20 mls of blood will be taken from patients aged 16 years and above, 10 mls from patients below 16 years old.
- 6. Once the patient is anaesthetised, two brush cytology scrapings using cytobrushes (provided) will be taken: one from the posterior pharynx including above and below the soft palate so that the adenoidal area is included, and a second separate brush scrape will be taken from the back of the tongue (base of tongue).
- 7. Tonsillectomy will then be performed and the tonsillar tissue will be placed in 10% buffered formalin and sent to the pathology department for paraffin embedding according to a specific protocol.
- 8. Stratified sampling will be employed to ensure that sufficient numbers of patients are recruited from all age groups, especially the age groups between 10 and 20 years old.

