12.2. ANALYSIS OF OUTCOME MEASURE

The statistical analyses will be described in detail in a statistical analysis plan (SAP). All of the tests will be two-sided with an alpha level of 0.05.

12.2.1. PRIMARY OUTCOME:

The overall prevalence will be estimated as the number of patients with HPV detected in tonsils divided by the total number of patients with available samples. An exact 95% confidence interval will be computed. The prevalence per age and gender group will be calculated similarly.

The relationship between prevalence and age will be explored using logistic regression with the age as a continuous covariate and gender and centre as categorical covariate. The number of degrees (one, two, three) of the model and possible variable transformation (e.g. log-transformation of age) could be determine based on graphical analysis of prevalence versus age relationship and on model fit criteria (e.g. AIC).

12.2.2. SECONDARY OUTCOME:

The overall prevalence will be estimated as the number of patients with HPV detected in oral fluid, oropharyngeal scrapes and urine samples divided by the total number of patients with available samples. An exact 95% confidence interval will be computed.

The prevalence per age and gender group will be calculated similarly. Prevalence rate will be compared among centres using a Cochran-Mantel-Haenszel test with stratification by age group.

Relationship between the prevalence of HPV in tonsils and the prevalence of HPV in oropharyngeal scrapes, oral fluid, and urine samples will be analysed by computing kappa coefficient. Specificity, sensitivity, positive predictive value and negative predictive value of HPV detection in the different sample types will be derived using the oral sample results as the reference.

Relationship between presence of anti-HPV L1 antibody in oral fluid samples and occurrence of HPV in tonsils and/or in oropharyngeal scrape samples will be analysed by computing kappa coefficiency. Specificity, sensitivity, positive predictive value and negative predictive value of anti-HPV L1 antibody assay will be derived using the oral sample results as the reference.

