The rate of HPV persistence will be calculated as the proportion of baseline HPV-positive patients who again test HPV-positive in oral fluid, fingertip/nail brushings and urine samples collected after approximately 3 - 6 months. The rate of oral HPV infection clearance will be calculated as the proportion of baseline HPV-positive patients who test HPV-negative in oral fluid, fingertip/nail brushings and urine samples collected after approximately 3 - 6 months.

HPV incidence will be calculated as the proportion of baseline HPV-negative patients who test HPV positive in oral fluid, fingertip/nail brushings and urine samples collected after approximately 3 - 6 months. Exact 95% confidence intervals will be computed.

Multi variable regression models will be used to calculate the odds ratios of different risk factors for having HPV DNA in the tonsil and in the oropharynx, Variables to be included in the model (e.g. serological markers and clinical risk factors such as HPV vaccination status, tobacco and alcohol use) will be selected on the basis of descriptive statistics/possible causal relationship and/or a stepwise approach. Analysis of results may be performed to identify a possible marker or combination of markers for screening for persistent HPV infections in the oropharynx.

Among females in the target age class for vaccination (12 to 24 years), exploratory analyses will compare the HPV prevalence rate in HPV vaccinated and non HPV vaccinated patients using a Fisher's exact test. Association between HPV vaccine and oral HPV infection will be assessed using a case-control approach. Cases will be patients with HPV positive oral sample and controls will be patients with HPV negative oral sample. The exposure to vaccine will be compared between the case and the control groups using logistic regression, OR and its 95% confidence interval will be derived.

Prevalence of HPV in tonsils will be described and compared between the current cohort and the comparison historical cohort using a Cochran-Mantel-Haenszel test with stratification by age group and gender.

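### The vaccine comparison in females aged 12–24 is fixed as an unadjusted Fisher test on HPV of unspecified type, and neither an age term nor HPV types are named for the accompanying logistic regression

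*Protocol*

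**What the plan says.** Section 12.2.2 of the Protocol plans two vaccine analyses in one paragraph.

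- **First analysis.** The paragraph opens "Among females in the target age class for vaccination (12 to 24 years" and goes on to say that "exploratory analyses will compare the HPV prevalence rate in HPV vaccinated and non HPV vaccinated patients", with Fisher's exact test as the method.
- **Second analysis.** This is a case-control approach: "Cases will be patients with HPV positive oral sample and controls will be patients with HPV negative oral sample". The model is given in the sentence that begins "The exposure to vaccine will be compared between the case and the control groups using logistic regression, OR and its 95% confidence interval will be". No covariate, matching factor or HPV type is listed.

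The general rule in section 12.2 is "All of the tests will be two-sided with an alpha level of 0.05", with further detail left to a SAP.

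The data that bear on the point are planned. Section 2.1.2 has the objective "To describe HPV-type distribution overall by age, gender, and sampling site". Section 7, item 2, requests from health and other records "confirmation of HPV vaccination status, including dates, number of doses and the type of vaccine given".

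Other between-group analyses name their control for age. The primary model has age, gender and centre as covariates. The centre comparison is a Cochran-Mantel-Haenszel test stratified by age group. The historical comparison is stratified by age group and gender.

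**The concern.** A Fisher test on a single two-by-two table carries no covariates. Naming it therefore fixes a crude comparison; it is not a detail left open. Section 12.3 treats patients aged 14 and under as non-exposed and older patients as exposed, and that boundary lies inside the 12–24 range. Table 1 also lists a study with 0% HPV at ages 7–12 and 5.2% at 13–20. Age may therefore be related to HPV within the comparison, and it may also be related to vaccination.

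The second issue is the outcome. A vaccine aimed at particular types is judged here on HPV without any stated type restriction, although type distribution is an objective and the vaccine given is requested.

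At stake is how the preliminary result on vaccination and oral infection is interpreted. A crude odds ratio could reflect age rather than the vaccine, and a real type-specific effect could look weak. The primary prevalence estimate is not affected.

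**Working it through.** The Protocol gives no sample size, power or effect size for the vaccine analyses, so there is no figure of its own to reproduce.

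**Step 1. Size of the group.** Table 6 plans 150 patients in each of the bands 10–14, 15–19 and 20–24. Assume ages are uniform within bands and half the patients are female.
- Ages 12–14: 3/5 × 150 × 0.5 = 45.
- Ages 15–19: 150 × 0.5 = 75.
- Ages 20–24: 150 × 0.5 = 75.
- Total: 195 females.

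**Step 2. Crude odds ratio when the vaccine does nothing.** Let n, c and p be the number, vaccine coverage and HPV prevalence in each age band. Prevalence in the vaccinated is Σncp / Σnc. In the unvaccinated it is Σn(1−c)p / Σn(1−c). The true odds ratio within each band is 1. All values of c and p below are assumptions, in the order 12–14 / 15–19 / 20–24.

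Worked example, coverage 90/90/50% and HPV 1/4/8%:
- Vaccinated: 40.5 + 67.5 + 37.5 = 145.5; events 0.405 + 2.70 + 3.00 = 6.1; prevalence 4.2%.
- Unvaccinated: 4.5 + 7.5 + 37.5 = 49.5; events 0.045 + 0.30 + 3.00 = 3.3; prevalence 6.8%.
- Crude odds ratio 0.60.

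| Coverage % | HPV % | Vaccinated vs unvaccinated | Crude odds ratio |
|---|---|---|---|
| 90/90/50 | 1/4/8 | 4.2% vs 6.8% | 0.60 |
| 80/85/65 | 1/4/8 | 4.6% vs 5.7% | 0.80 |
| 90/90/50 | 3/5/6 | 4.7% vs 5.6% | 0.84 |
| 80/85/65 | 3/5/6 | 4.8% vs 5.2% | 0.93 |
| 80/80/30 | 0/5/10 | 4.4% vs 7.8% | 0.55 (0.545) |
| 10/80/80 | 0/5/10 | 7.2% vs 3.2% | 2.4 |
| 80/80/30 | 5/6.5/8 | 6.3% vs 7.4% | 0.85 |
| 10/80/80 | 5/6.5/8 | 7.2% vs 6.0% | 1.22 |
| 77/77/77 | any | equal | 1.0 |
| any | 6.5/6.5/6.5 | equal | 1.0 |

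The direction follows the coverage pattern. If the oldest band is least vaccinated, the bias is towards apparent protection. If the youngest band is least vaccinated, it is towards apparent harm.

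**Step 3. Dilution by other types.** If vaccine types make up a share s of positives, efficacy against them is VE, and other types are unaffected, the risk ratio for HPV of any type is 1 − s × VE. With VE 90% (assumed):
- s = 30%: 1 − 0.27 = 0.73.
- s = 50%: 1 − 0.45 = 0.55.

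**Step 4. What a type-specific outcome does to power.** Exact Fisher power, two-sided 0.05, with an assumed split of 150 vaccinated and 45 unvaccinated and VE 90%:

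| Share s | HPV in unvaccinated | Any type | Vaccine types |
|---|---|---|---|
| 50% | 6.5% | 11% | 17% |
| 50% | 10% | 17% | 35% |
| 50% | 31% | 49% | 90% |
| 20% | 6.5% | 4.6% | 2.0% |

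The prevalences 6.5% and 31% are the literature figures in section 12.3, and 10% is the top of the range given there. A narrower outcome usually gains power here, but not always.

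**The case against.** The strongest reply is that these analyses are labelled exploratory, the objective is preliminary, and the SAP may add what is missing. Much of that stands.

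- **Logistic model.** A reader might infer that it contains vaccine exposure only. The text lists no covariates but does not exclude them, and a covariate list can properly be left to a SAP. Only the Fisher test is fixed as unadjusted.
- **Population.** A reader might infer that males or patients outside 12–24 enter the case-control analysis as unexposed. The case-control sentences follow in a paragraph that opens with females aged 12–24, so the natural reading keeps the restriction. A clarifying phrase is enough.
- **Direction.** A reader might infer that the bias favours the vaccine because unvaccinated women are older. No coverage by age is given, and Step 2 shows that it can run either way.
- **Numbers.** A reader might infer 150 vaccinated and 45 unvaccinated. The 150 in section 12.4 belongs to the historical comparison, whose Table 7 uses 1100 per group; the 195 derives from the 925 in Table 6. The split in Step 4 is therefore only an assumption.
- **Typing.** The type-distribution objective implies typing, but nowhere is it said that every sample is typed.
- **Noise.** In the worked example there are about 9 events, and an odds ratio of 0.60 has an approximate 95% interval of 0.15 to 2.4. The possible bias is small against that.

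Restriction to one sex and to ages 12–24 is also partial control. What does not stand is reliance on the separate multivariable risk-factor model. Vaccination status is only a candidate there, age is not among the named examples, and selection may be stepwise. Low precision also does not excuse a bias that costs little to remove.

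**Conclusion.** The point holds in a limited form. The Protocol fixes a crude test of HPV of unspecified type across an age range that spans its own exposure boundary, while its primary model, centre comparison and historical comparison control for age. The crude result is biased if coverage and prevalence both vary with age. With no vaccine effect, the odds ratio is 0.60 to 0.93 in the first four scenarios, about 0.55 to 2.4 across the wider set, and 1.0 if either factor is flat. Those inputs are assumed, as are the type share and efficacy behind the diluted risk ratio of 0.73 to 0.55. That the outcome is HPV of any type is inferred from the absence of a restriction.

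A reader might go further and conclude that the vaccination objective cannot be interpreted at all. The documents do not support that: the objective asks only for preliminary data, and the analyses are exploratory. The change is worth making because it is cheap and improves how a secondary result can be read.

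**What to change.** In section 12.2.2, or in the SAP with a matching change to the Fisher sentence:

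1. State that both exploratory vaccine analyses are in females aged 12–24.
2. Replace or supplement the Fisher test with an age-adjusted estimate and its interval: an exact age-stratified analysis, or Firth logistic regression with age, because events are few. Name age in the case-control model as well.
3. Make detection of vaccine-type HPV the main outcome for the vaccine question, with a stated rule for which types count in unvaccinated patients. Report HPV of any type as supportive and non-vaccine types as a descriptive negative control.
4. Optionally, add sexual history as a sensitivity analysis in those old enough to complete the questionnaire.

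The cost is wording, since age, HPV type and vaccine type are already planned data, although vaccine records may be incomplete. The downside is fewer events for the type-specific outcome, wide intervals and no guaranteed gain in power. The results should still be presented as preliminary.

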12.3. SAMPLE SIZE CONSIDERATIONS

An analysis of current literature suggests that in a population recruited between 1990 and 2000, the prevalence of oral HPV was about 6.5%, varying from 0% - 10%. However, in an analysis of oropharyngeal scrapes and oral washings, the prevalence of HPV detection was much higher at 31%.

Pilot data of patients having tonsillectomy at University Hospital Coventry over two 3-month time periods are shown below in table 3. The number of tonsillectomy operations performed at the Heart of England NHS Foundation Trust - is approximately 50% of that for University Hospital Coventry quoted below.

Table 5: The number of tonsillectomy operations performed at University Hospital Coventry.

Age Group*	Number of Monthly recruitment (%)		
0-4	7 (12%)		
5-9	12 (20%)		
10-14	7 (12%)		
15-19	10 (17%)		
20-24	6 (10%)		
25-29	5 (8%		
30-34	4 (7%)		
35-39	5 (8%)		
40-44	1 (2%)		
45-49	1 (2%)		
50-69	1 (2%)		
Total	59		

^{*}There was an equal distribution of males and females in the group.

We plan to enrol 925 patients. The precision of the overall prevalence estimate that would be achieved with such a number is summarised in Figure 1 for prevalence ranging from 1 to 31 %. For example, if the observed prevalence is 10 %, the 95 % confidence interval for the overall population will be 8.4 to 11.8 % corresponding to a relative precision of 17 %.

[figure not shown]

Figure 1: Precision (95% confidence interval) of the prevalence estimate versus the prevalence observed in a random sample of 1250 patients.

We will also undertake a stratified sampling strategy to allow comparisons between those aged 14 and under (non-exposed, approximately one third of the cohort), and patients over 14 years of age (exposed) to allow the determination of the age of acquisition of infection and the optimal age of start of vaccination. The stratified sampling strategy will recruit patient subgroups as follows:

Table 6: The stratified sampling strategy for patient recruitment.

Age group	Sample size (%)		
0-4	150 (16.5%)		
5-9	150 (16.5%)		
10-14	150 (16.5%)		
15-19	150 (16.5%)		
20-24	150 (16.5%)		
25-34	100 (11%)		
35-44	60 (5.5%)		
45-65	15 (1.0%)		
Total	925		

[figure not shown]

Figure 2: Precision (95% confidence interval) of the prevalence estimate versus the prevalence observed in a random sample of 100, 150, and 250 patients.

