1.4. GAPS IN THE LITERATURE

The vaccination of girls only may not protect males, especially if herd immunity is not achieved due to incomplete uptake of the vaccine in girls. Therefore, in view of the recent rise in HPV-oropharyngeal carcinoma, some experts are raising the possibility of the vaccination of boys as well as girls. Yet, to date insufficient data is available on oropharyngeal HPV infection to allow the accurate assessment of the need for and cost effectiveness of including boys in the HPV vaccination programmes in the EU.

Furthermore, there is little information on the prevalence of HPV infection in the mouth in the general population or on the age and gender distribution of this infection. The data that is available consists of small studies. These are usually retrospective and most of the study cohorts are over ten years old – therefore most of the prevalence data available is at least ten years old. Furthermore, the studies used a variety of sample types and different HPV detection techniques. Therefore the results are widely varying with reported HPV prevalence rates in the mouth between 0% and 31%.

Table 1: Frequency with which high-risk HPV types were detected in oral exfoliated cell samples using PCR methods (> 10 cases).

Study	City	Period of patient accrual	Age range	HPV detection	Type of oral sample	No of samples	HPV+ rate
D'souza 2007	Baltimore, USA	2000-5	<50yrs-34%, >50yrs-66%	PCR	Oral rinse and brush	200	6%
Smith 2007	Iowa , USA	n/a	2-20	PCR	Oral exfoliated cells	1235	1.9%
Rintala 2006	Finland	N/A	28	PCR	Scrapings	462	15-27%
Smith 2004	Iowa, USA	1994-97	18-70, 34% <55	PCR	Oral exfoliated cells	333	10.8%
Summersgill 2001	Iowa	<2001	<20	PCR	Swabs or oral rinses	268	8.7% <7yrs, 0% 7-12, 5.2% 13-20
Koch 1997	Denmark	<1997	0-17	PCR	Oral rinses	392	0.26%
Puranen 1996	Finland	1981-96	0.3-11.6	PCR	Oral scrapings	98	31.6%
Rice 1996	London	<1996	3-11	PCR	Buccal swabs	267	17%
Jennison 1990		<1990	preschool	PCR	Oral scrapings	21	24%

Table 2: Frequency with which high-risk HPV types were detected in tonsillectomy samples using PCR methods (> 10 cases).

Study	Year	City	Period of patient accrual	Age range	HPV detecti on	Number of samples	Number positive for HPV
Klinkenberg	2010	Netherlands	1997-98	29.2	PCR	195	2 (1%)
Ernster	2009	USA	1979-82; 1997- 2001	> 21 years	PCR	226	0 (0%)
Kim	2007	Korea	1995-2005	NS	RT-PCR	69	3 (4%)
Sisk	2006	USA	AO	paediatric patients	PCR	50	1 (2%)
Ribeiro	2006	Brazil	NS	2-13 years	PCR	64	5 (7.8%)

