2.2. OUTCOME MEASURES

2.2.1. PRIMARY OUTCOME

Occurrence of HPV in tonsil samples

[figure not shown]

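### Section 12.3 illustrates the precision of the tonsil estimate only at 10% prevalence, above the overall rate of every tonsil series in Table 2, and the quoted interval and 17% belong to 1250 patients, not 925

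*Protocol*

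**What the plan says.** Protocol section 2.2.1 defines the primary outcome as "Occurrence of HPV in tonsil samples", with no restriction by HPV type. Section 12.2.1 gives the estimator, whose denominator is everyone with a sample to test: "The overall prevalence will be estimated as the number of patients with HPV detected in tonsils divided by the total number of patients with available". It adds that "An exact 95% confidence interval will be computed".

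Section 12.3 cites two background prevalences. The first is that "the prevalence of oral HPV was about 6.5%, varying from 0% - 10"%. The second follows as a contrast: "However, in an analysis of oropharyngeal scrapes and oral washings, the prevalence of HPV detection was much higher at 31"%. Neither is labelled as a tonsil figure, and the section does not refer to Table 2. It then states "We plan to enrol 925 patients", points to Figure 1 for prevalences from 1 to 31%, and gives one worked case: "if the observed prevalence is 10 %, the 95 % confidence interval for the overall population will be 8.4 to 11.8"%, described as a relative precision of 17%. The caption of Figure 1 names 1250 patients. Figure 2 is captioned for samples of 100, 150 and 250.

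The protocol's tonsil data are in section 1.4, under the title "Table 2: Frequency with which high-risk HPV types were detected in tonsillectomy samples using PCR methods (> 10 cases"). Section 12.4 and Table 7 take historical tonsil prevalences of 2, 5 and 8%, with 4.1, 8.1 and 11.6% as the matching detectable values in the new cohort.

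**The concern.** Relative precision is the measure the protocol quotes, and it worsens as prevalence falls. The only precision put into words is at a prevalence higher than the overall rate of any tonsil series the protocol lists. Figure 1, the only other source for the whole cohort, is captioned for a larger sample than the one planned. The text therefore gives no precision that is correct for 925 patients at a tonsil-range prevalence.

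The overall tonsil prevalence is the first part of the primary objective, and section 1.5 ties the study to whether HPV is common enough to justify vaccinating boys. Someone judging whether 925 patients are enough for that would take away a more favourable figure than the design provides.

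**Working it through.** **Inputs.** Planned patients 925; worked example 10%, 8.4 to 11.8%, 17%; Figure 1 caption 1250 (all section 12.3). Nine tonsil series (Table 2). Prevalence scenarios (Table 7). Exact interval (section 12.2.1).

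**Method.** For x positives of n, the Clopper-Pearson limits are the 2.5% quantile of Beta(x, n − x + 1) and the 97.5% quantile of Beta(x + 1, n − x). Relative precision = (upper − lower) / 2 ÷ prevalence.

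**1. The plan's own figure**
- 125/1250 (10%): 8.39 to 11.80%; half-width 1.70 points; 1.70/10 = 17.0%. This is the quoted result.
- 10% of 925: 8.14 to 12.12%; half-width 1.99 points; 19.9%.
- 10% of 1000 (the ceiling in the study summary): 8.21 to 12.03%; 19.1%.
- 10% of 1100 (Table 7): 8.29 to 11.93%; 18.2%.
- Other interval methods do not rescue it: at 925 and 10%, Wilson gives 8.23 to 12.10% and Wald 8.07 to 11.93%.

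Of these sample sizes, only 1250 reproduces the quoted interval.

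**2. What Table 2 shows**
- Samples: 195 + 226 + 69 + 50 + 64 + 106 + 206 + 48 + 14 = 978.
- Positives: 2 + 0 + 3 + 1 + 5 + 6 + 13 + 0 + 0 = 30.
- Crude pool 30/978 = 3.07%; simple mean of the nine rates 3.02%; highest series 5/64 = 7.8%.

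**3. Exact precision with 925 patients**

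| Prevalence | Positives | 95% CI | Half-width (points) | Relative precision |
|---|---|---|---|---|
| about 3% | 29 | 2.1 to 4.5% | 1.2 | 38% |
| about 5% | 46 | 3.7 to 6.6% | 1.5 | 29% |
| 6.5% | 60 | 5.0 to 8.3% | 1.6 | 25% |
| 7.8% | 72 | 6.1 to 9.7% | 1.8 | 23% |
| 8% | 74 | 6.3 to 9.9% | 1.8 | 22 to 23% |
| about 10% | 92 | 8.1 to 12.1% | 2.0 | 20% |

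At the Table 7 values for the new cohort (4.1, 8.1 and 11.6%), relative precision is about 33%, 22% and 18%. With 925 patients, 17% is first reached at a prevalence of about 13%.

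**4. Splitting the gap.** From 17% to 20% is the patient number (1250 against 925). From 20% to 38% is prevalence (10% against 3.1%). Correcting the patient number alone does not remove the problem: even 1250 patients at about 3% (38/1250) give 33%.

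**The case against.** The other side has a good deal in its favour.

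- **The 10% is conditional.** It is introduced as an example within a 1 to 31% range that includes 3%. A reader might infer that the primary estimate is promised 17% precision, or that 925 was derived from an oral prevalence. The text says neither: no formula leads to 925, and no relative-precision target is set that could be missed.
- **Absolute precision improves at lower prevalence.** The half-width is about 1.2 points at 3.1% against 2.0 at 10%.
- **3.1% is at the low end.** Table 2 is headed high-risk types, whereas the outcome has no type restriction. The pool is also older than the planned cohort: three adult series without a positive supply 226 + 48 + 14 = 288 of the 978 samples, while Table 6 plans 450 of 925 patients under 15. The three paediatric series give (1 + 5 + 6)/(50 + 64 + 106) = 12/220 = 5.5%, where 925 patients would give about 28%. The footnote to Table 2 mentions low-risk types and 11.5% in preschool children for one series, and Table 7 allows 11.6%. A prevalence of 10% is not excluded.
- **The word oral may be loose.** The 6.5% is set against scrapes and washings, and its 0 to 10% range is nearer to Table 2 (0 to 7.8%) than to Table 1 (0.26 to 31.6%).
- **Age bands are covered.** Figure 2 already includes samples of 150.

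All of this stands, and it limits the point. It does not rescue the worked figure, which is wrong for 925 patients at 10% itself and is not reached even at 11.6%. If the 6.5% does mean tonsil, it is still about twice the crude Table 2 average, so the two places need reconciling.

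**Conclusion.** The point holds as a correction to a stated property of the design. The quoted 8.4 to 11.8% and 17% do not describe 925 patients, and the one prevalence chosen for illustration lies above the overall rate of every tonsil series tabulated. Depending on which tonsil prevalence applies, the relative precision with 925 patients is about 38% (3%), 29% (5%) or 22 to 23% (8%).

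This assumes an exact interval, all 925 patients contributing a tonsil result (fewer would widen it), and relative precision taken as the half-width over the estimate, the definition that reproduces the protocol's 17%. The Figure 1 finding rests on its caption, since the plotted curve was not available.

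A reader might go further and conclude that the study is too small, or that age-by-sex tonsil estimates must be pooled. The documents do not support either step: there is no precision target to fail, and section 12.2.1 promises estimates by age and gender group without committing to crossed cells.

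**What to change.** In section 12.3:

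1. Recompute the worked example for 925 patients (at 10%: 8.1 to 12.1%, relative precision about 20%), and redraw and recaption Figure 1 for 925.
2. Beside the 10% case, state the precision at tonsil prevalences of about 3% (2.1 to 4.5%, 38%), 5% (3.7 to 6.6%, 29%) and 8% (6.3 to 9.9%, 22 to 23%).
3. Say whether the 6.5% (0 to 10%) refers to oral or tonsil samples, and reconcile it with Table 2. If it is oral, attach it to the secondary oral outcomes.

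The cost is a revision of section 12.3 and one figure, with a less favourable stated precision. Recruitment, the analysis and the age-by-sex reporting stay as they are.
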